4.2.3 Concomitant Medications and Non-Drug Therapies

All concomitant medications will be coded using the World Health Organization (WHO) medication dictionary. All concomitant non-drug therapies will be coded using the MedDRA dictionary. A concomitant medication/therapy will be defined as any therapy that was taken on or after the day of the first dose of study drug. This includes therapies that start prior to the initiation of the first dose if their use continues on or after the date of first dose. To define concomitant use for therapies with missing start or stop dates, the following additional criteria will be used:

- if both the start and stop dates of a therapy are missing, that therapy will be considered concomitant.
- if the start date of a therapy is missing and the stop date of that therapy fall on or after the date of the first dose, that therapy will be considered concomitant.
- if the start date of a therapy is prior to the date of the first dose and the stop date of that therapy is missing and the therapy is listed as continuing, that therapy will be considered concomitant, or
- if the start date of a therapy is prior to the date of the first dose and the stop date of that therapy is missing and the therapy is not listed as continuing, that therapy will be considered non-concomitant.

For a therapy with a partial start date, the year/month of the therapy date will be compared to that of the first dosing date to determine whether the therapy is concomitant.

The number (%) of subjects taking concomitant medication and non-drug therapies will be summarized. Non-drug therapies will be presented by treatment group. Concomitant medications and non-drug therapies will be listed.

AD symptomatic medications taken concomitantly at baseline are defined as AD symptomatic medications that were being taken at the time of the first dose, i.e., started prior to the first dose and continued until after the first dose. The number (%) of subjects taking AD symptomatic medications concomitantly at baseline will be summarized. In addition, number of subjects using Cholinesterase inhibitors only, Memantine only, or both at baseline will be summarized. Subjects who have any change in AD symptomatic medications after the initiation of study treatment will be summarized by the timing of change, i.e., the number of subjects changing between Day 1 and Week 26, the number of subjects changing between Week 26 and Week 50, etc. The summary for AD symptomatic medication use during study

Final V1.0

will be presented by treatment group. The start and stop date of AD symptomatic medication will be listed for these subjects.

4.2.4 Protocol Deviations

Protocol deviations identified during site monitoring will be captured in a Protocol Deviation log and categorized as major or minor deviations based on Protocol Deviation Classification (see Appendix 6.2). The major protocol deviations will be summarized (presented by treatment group). Listings will be generated for the major and minor protocol deviations, respectively. A listing will be generated for subjects with incorrect stratification ApoE status, i.e., treatment stratification ApoE $\epsilon 4$ status in IXRS different from the laboratory ApoE $\epsilon 4$ status.

4.2.5 Study Drug Exposure and Study Drug Compliance

A summary table of study drug exposure and compliance will be provided. Number of infusions (aducanumab or placebo) received will be summarized as a categorical variable (categories as integers from 1 to 20, and 1-5, 6-10, 11-15, and 15-20) as well as a continuous variable. Number of weeks on study treatment (aducanumab or placebo), calculated as (date of last dose – date of first dose + 29)/7, will be summarized as a categorical variable (every 8 weeks from 0 to >= 72 weeks) as well as a continuous variable. Percentage of study treatment taken up to the last dose, calculated as (the actual number of infusions / by the number of infusions a subject is expected to take until the date of last infusion)*100, will be summarized as a continuous variable. This table will be presented by treatment group.

Due to the use of titration regimen in the study and possible dose reduction due to ARIA, another summary table will be provided including the following information: number of total infusions (categories of 1-5, 6-10, 11-15, and 15-20) as well as a continuous variable, number of infusions at each dose level (1 mg/kg, 3 mg/kg, 6 mg/kg and 10 mg/kg, respectively) summarized as a categorical variable as well as a continuous variable, number of subjects with dose increase (placebo to 1 mg/kg, 1 to 3 mg/kg, 3 to 6 mg/kg and 6 to 10 mg/kg, respectively), number of subjects with dose reduction (1 mg/kg to placebo, 3 to 1 mg/kg, 6 to 3 mg/kg and 10 to 6 mg/kg, respectively), maximum dose level received, and cumulative dose (as a continuous variable). This table will be presented by treatment group stratified by ApoE status.

A listing of study drug administration records, including dose level at each infusion, cumulative number of infusions and cumulative dose will be provided. A listing of aducanumab lot numbers will be provided.

A listing of study drug administration records for placebo subjects who received any doses of active treatment will be provided.

4.3 Efficacy Analysis

4.3.1 General Considerations

For efficacy endpoints, the following treatment groups of aducanumab (per randomization) will be evaluated and compared with placebo:

- Aducanumab high-dose (10 mg/kg in ApoE ε4 carriers [including 6 mg/kg for subjects enrolled under protocol versions 1-3 who do not have the opportunity to uptitrate to 10 mg/kg prior to completing Week 78 of the study] and 10 mg/kg in ApoE ε4 non-carriers).
- Aducanumab low-dose (3 mg/kg in ApoE ε4 carriers and 6 mg/kg in ApoE ε4 non-carriers).

All efficacy analyses will be performed on the ITT population. In addition, the primary and secondary endpoints will also be performed on the per-protocol population. The efficacy analysis will be presented by treatment group (per randomization), i.e., aducanumab high-dose, aducanumab low-dose and placebo (analysis display A in Appendix 6.1).

The primary, sensitivity and supplementary analyses for the primary and secondary endpoints are listed in Table 2.

Table 2. Analysis for Primary and Secondary Endpoints

Endpoint	Analysis	Analysis Population	SAP Section
CDR-SB	Primary: Analysis of change from baseline at Week 78 (MMRM)	ITT	4.3.2.1
	Sensitivity: Pattern mixture model (ANCOVA)	ITT	4.3.2.2.1
	Sensitivity: Copy increment from reference method (ANCOVA)	ITT	4.3.2.2.2
	Sensitivity: Imputation by natural disease progression (ANCOVA)	ITT	4.3.2.2.3
	Sensitivity: Tipping point analysis (ANCOVA)	ITT	4.3.2.2.4
	Supplementary: Censoring after intercurrent events (MMRM)*	ITT	4.3.2.3.1
	Supplementary: Per-protocol analysis (MMRM)	Per-protocol	4.3.2.3.2
	Supplementary: Responder analysis (Logistic regression)	ITT	4.3.2.3.3
	Supplementary: Slope analysis (MMRM)	ITT	4.3.2.3.4
	Supplementary: Divergence effect analysis (MMRM)	ITT	4.3.2.3.5
MMSE,	Primary: Analysis of change from baseline at Week 78 (MMRM)	ITT	4.3.3.1, 4.3.3.2, 4.3.3.3

CONFIDENTIAL

Biogen		Statistical Analysis Plan Placebo-Controlled Period		Final V1.0	
ADAS-Cog 13, ADCS-ADL-	Sensitivi	ry: Pattern mixture model (ANCOVA)	ITT	4.3.3.4	
MCI	Supplem (MMRM	entary: Censoring after intercurrent events)*	ITT	4.3.3.4	
	Supplementary: Per-protocol analysis (MMRM)		Per-protocol	4.3.3.4	
Suppleme		entary: Slope analysis (MMRM)	ITT	4.3.3.4	
	Supplem	entary: Divergence effect analysis (MMRM)	ITT	4.3.3.4	

^{*} Analysis excludes data collected after the following intercurrent events: (1) premature discontinuation of the study treatment and (2) any change to concomitant AD symptomatic medications during the study. All other analyses will include data collected after intercurrent events [ICH E9 (R1) Addendum 2017].

Visit windows for mapping efficacy endpoint

For efficacy data that are summarized or analyzed by visit, data collected on all scheduled visits and all unscheduled visits will be mapped to an appropriate analysis visit using the windowing scheme shown in Table 3. If there are 2 or more assessments available in the same analysis window for a subject, the assessment that is closest to the target visit day will be used for analysis. If there are 2 or more assessments in the same analysis window with the same distance from the target visit day, the later assessment will be used.

Table 3. Visit Windows for Efficacy Endpoints

Target visit day	Analysis visit window
1	Most recent non-missing pre-dose value
183	[92, 266]
351	[267, 448]
547	[449, the end day of the placebo-controlled period *]
	1 183 351

^{*} The end day of the placebo-controlled period is the last day before the first infusion in LTE for subjects who enter LTE, and is the last day in study for subjects who do not enter LTE.

Handling of missing items for scales

If any of the individual items for the primary and secondary endpoints is missing, the total score of the corresponding endpoint will be imputed by prorating the observed scores [van Ginkel 2010].

For ADAS-Cog13, if 3 or fewer of 13 items (<25%) are missing, the total score will be imputed by the following algorithm: Total score = total score from the completed items * [maximum total score (=85) / maximum total score for the completed items]. The imputed number will be rounded up to the nearest integer. If more than 3 items are missing, the total score of ADAS-Cog 13 at that visit will be considered missing.

For ADCS-ADL-MCI, if 4 or fewer of 18 items (<25%) are missing, the total score will be imputed by a similar algorithm as that for ADAS-Cog 13. The imputed number will be

Final V1.0

rounded up to the nearest integer. If more than 4 items are missing, the total score for ADCS-ADL-MCI at that visit will be considered missing.

The same imputation algorithm will be applied to CDR-SB and MMSE, if only 1 box (of 6) of CDR is missing or if only 2 or fewer items (out of 11) are missing for MMSE. If the score from more than 1 box of CDR or more than 2 items of MMSE is not available, the CDR-SB or MMSE at that visit will be considered missing.

The total score of the tertiary endpoint NPI-10 will be imputed using the same prorating principle if only 1 item (out of 10) is missing. For EQ-5D and mPDQ-20, if any item is missing, any total or sum involving that item will be considered missing.

Considerations for multiple comparison adjustments

A sequential (closed) testing procedure will be used to control the overall Type I error rate due to multiple comparisons for the primary endpoint. The order of treatment comparisons is as follows: aducanumab high-dose versus placebo and aducanumab low-dose versus placebo. All comparisons after the initial comparison with p > 0.05 will not be considered statistically significant.

Secondary endpoints have been rank prioritized, in the order shown in Section 1.2. In order to control for a Type I error for the secondary endpoints, a sequential closed testing procedure will be used and will include both the order of the secondary endpoints and treatment comparisons. Specifically, for each of the secondary endpoints, a sequential (closed) testing procedure, as for the primary endpoint, will be used to control the overall Type I error rate due to multiple treatment comparisons. If statistical significance is not achieved for 1 or 2 treatment comparisons, all endpoint(s) of a lower rank will not be considered statistically significant for that 1 or 2 treatment comparisons, respectively.

There will be no multiple comparison adjustments for the sensitivity and supplementary analyses for the primary and secondary efficacy endpoints, the tertiary efficacy endpoints, the subgroup analyses or the additional analyses.

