2 STUDY DESIGN

2.1 Study Overview

Study 221AD301 (ENGAGE) is a multicenter, randomized, double-blind, placebo-controlled, parallel-group study in subjects with early AD, including mild cognitive impairment (MCI) due to AD and a subset of mild AD, followed by an optional dose-blinded long-term extension (LTE) period of up to 5 years. Approximately 1605 subjects will be enrolled across approximately 150 centers globally. The primary study objective is to evaluate the efficacy of monthly doses of aducanumab on the CDR-SB relative to placebo. Secondary objectives include assessment of the effect of monthly doses of aducanumab on clinical progression as compared to placebo. The safety of monthly doses of aducanumab will also be evaluated.

Table 1: Dosing Scheme for Aducanumab by Treatment Group and ApoE ε4 Carrier Status: Placebo-Controlled Period

Dose (every 4 weeks)			2	3	4	5	6	7 to 20
Treatment Group Stratified by ApoE Status ²]	Dose (m	g/kg)		
High Dose - ApoE ε4 (+)		1	1	3	3	6	6	10 ¹
	High Dose - ApoE ε4 (-)	1	1	3	3	6	6	10
Low Dose	Low Dose - ApoE ε4 (+)	1	1	3	3	3	3	3
	Low Dose - ApoE ε4 (-)	1	1	3	3	3	3	6
Placebo	Placebo - ApoE ε4 (+)	saline						
	Placebo - ApoE ε4 (-)	saline						

¹⁰ mg/kg is the target dose for all ApoE ε4 carriers assigned to the aducanumab high-dose group. Subjects enrolled under protocol versions 1-3 and assigned to the previous high-dose of 6 mg/kg will be titrated to 10 mg/kg upon receipt of at least 2 doses at 6 mg/kg.

Subjects will be randomized in a 1:1:1 ratio to 1 of the 3 treatment groups: aducanumab high dose, aducanumab low dose and placebo, with stratification based upon their apolipoprotein E4 (ApoE &4) carrier status (carrier/non-carrier) and site. During the placebo-controlled period, subjects will receive infusions of aducanumab or placebo approximately every 4 weeks for approximately 18 months (a total of 20 doses). Dose levels may be different in the same treatment group based upon subjects' ApoE &4 carrier status, and specifically, ApoE &4

² ApoE ε4 status recorded in the Interactive Voice/Web Response System (IXRS).

Final V1.0

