4 STATISTICAL ANALYSIS METHODS

4.1 General Considerations

This statistical analysis plan (SAP) only covers the analyses for the primary, secondary and tertiary objectives for the placebo-controlled portion of the study. Hereafter, the placebo-controlled portion of the study will be referred to as "the study" in the rest of this SAP (e.g.,

Final V1.0

completion of the study means completion of the placebo-controlled portion). A separate SAP will be prepared for the analyses of the LTE period and integrated analyses across both portions of the study. The analyses of additional exploratory endpoints will be documented separately.

Summary tables will be presented using descriptive summary statistics. For continuous variables, summary statistics will generally include: number of subjects with data, mean, standard deviation, median, 25% percentile, 75% percentile, minimum and maximum. For categorical variables, this will generally include: number of subjects randomized or dosed, number with data, and the percent of those with data in each category.

There are two types of analysis displays for tables: by treatment group (analysis display A in Appendix 6.1) and by treatment group stratified by ApoE status (analysis display B in Appendix 6.1; here ApoE status refers to the status recorded in IXRS [see Table 1 for correspondence between treatment groups and treatment groups stratified by ApoE status]). The analysis display for each analysis will be defined in each section. All the listings will be presented by treatment group stratified by ApoE status, unless otherwise specified.

Unless otherwise specified, baseline value is defined as the most recent non-missing measurement collected prior to the first dose. Change from baseline will be defined as post-baseline value minus baseline value.

Unless stated otherwise, all statistical tests will be 2-sided with statistical significance level of 0.05.

The statistical software, SAS® will be used for all summaries and analyses.

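### The secondary-endpoint testing rule does not strongly control Type I error: two branches can run at the full 0.05, so the error rate within the secondary family can reach about 9-10%

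*SAP*

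**What the plan says.** All of this is in SAP section 4.3.1, under the multiple-comparison heading, with the significance level in section 4.1.

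- Level: "all statistical tests will be 2-sided with statistical significance level of 0.05".
- Primary endpoint: "The order of treatment comparisons is as follows: aducanumab high-dose versus placebo and aducanumab low-dose versus placebo", and "All comparisons after the initial comparison with p > 0.05 will not be considered statistically significant".
- Secondary endpoints: "Secondary endpoints have been rank prioritized, in the order shown in Section 1.2", which gives MMSE, ADAS-Cog 13, ADCS-ADL-MCI.
- Stated purpose: "In order to control for a Type I error for the secondary endpoints, a sequential closed testing procedure will be used". The SAP adds that "a sequential closed testing procedure will be used and will include both the order of the secondary endpoints and treatment comparisons".
- Operative rule: within each secondary endpoint the high dose is tested before the low dose, as for the primary. Then: "If statistical significance is not achieved for 1 or 2 treatment comparisons, all endpoint(s) of a lower rank will not be considered statistically significant". The sentence ends by confining this to the same one or two dose comparisons, respectively.

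The SAP promises control for the primary endpoint and, separately, for the secondary endpoints. It states no single 5% rate across both. The section does not say whether secondary testing depends on the CDR-SB result.

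**The concern.** The block on lower ranks is dose-specific. If high-dose MMSE fails, low-dose MMSE cannot be claimed either, and both doses stop; that is the case of two failed comparisons. If only low-dose MMSE fails, only the low dose stops and the high dose goes on to ADAS-Cog 13; that is the case of one. This reading gives the closing word (respectively) its meaning.

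So after a high-dose MMSE success two hypotheses are open at once: low-dose MMSE and high-dose ADAS-Cog 13. Each is tested at 0.05 and neither waits for the other. A closed procedure needs a 0.05-level test of the intersection of those two nulls. Rejecting when either p-value is at most 0.05 is not such a test. The same fork recurs one rank down, between low-dose ADAS-Cog 13 and high-dose ADCS-ADL-MCI.

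This rule decides which secondary results may be reported as statistically significant. The unfavourable case is also a realistic one for this design: the high dose works on the leading endpoint and the low dose does not.

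**Working it through.** **Inputs.** Two-sided 0.05 per test (section 4.1). Equal allocation (section 2.1: "Subjects will be randomized in a 1:1:1 ratio to 1 of the 3 treatment groups"). Order of doses and endpoints as above. The correlation ρ between endpoints is not in the SAP; it is assumed equal for all pairs and varied from 0 to 1.

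**Correlation between doses.** With equal arms of size n and common variance σ², each dose-minus-placebo difference has variance 2σ²/n. The two share the placebo arm, so their covariance is σ²/n. The correlation on one endpoint is (σ²/n)/(2σ²/n) = 0.5. Across doses and across endpoints it is 0.5ρ.

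**Primary family (the plan's own figure).** High then low, stopping at the first p > 0.05, gives a simulated maximum of 0.050. The stated 0.05 is reproduced.

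**Secondary family, worst case.** Let the high-dose MMSE effect be real and rejected with near certainty, with low-dose MMSE and high-dose ADAS-Cog 13 null. A false claim occurs if either null is rejected. For independent tests this is 1 − 0.95² = 0.0975. By simulation:

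| ρ | Error within secondary family |
|---|---|
| 0 | 9.7% |
| 0.5 | 9.6% |
| 0.7 | 9.4% |
| 0.9 | 9.2% |
| 1 | 9.1% |

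The result hardly depends on ρ, because the two tests correlate at only 0.5ρ. Counting only false claims in favour of the drug, with the high-dose CDR-SB and MMSE effects real, the secondary-family rate is 4.5-5.0% against a nominal 2.5%.

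**Secondary family, other cases.**
- Global null: 5.0% at every ρ, because nothing opens until high-dose MMSE is falsely rejected.
- High-dose CDR-SB and MMSE tests with 90% and 80% power (assumed): 7.2% at ρ = 0, falling to 5.4% at ρ = 1. As a rough check at ρ = 0, 0.80 × 0.0975 = 7.8%. The simulated value is lower because low-dose false rejections in the unfavourable direction tend to accompany weaker high-dose results.

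**Primary and secondaries counted as one family.** With high-dose CDR-SB and MMSE real and the rest null, low-dose CDR-SB is a third open test: 1 − 0.95³ = 0.1426 if independent. Simulation gives 14.3% at ρ = 0, 13.4% at 0.5, 12.4% at 0.7 and 11.0% at 0.9. At 90% and 80% power it is 10.8% at ρ = 0, falling to 5.9% at ρ = 1.

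**Effect of a condition on CDR-SB.** Requiring only that high-dose CDR-SB be significant leaves the combined maximum at up to 14.2%. A dose-by-dose requirement, with the branching kept, still leaves 9.1-9.7%. The branching is the main driver.

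**One fixed sequence at 0.05.** The family error is at most 5% by construction: the first true null reached is tested at 0.05, and nothing later is tested unless it is rejected.

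**The case against.** The best defence is that the figures are maxima. They need near-certain rejection of the real high-dose MMSE effect; under the global null the secondary family holds at 5%, and at plausible power the excess is 0.4 to 2.2 points. The primary family is correctly controlled, so the main conclusion of the trial is untouched. All of that stands, and it limits the severity. It does not rescue the rule, because strong control means 5% in every configuration of true and false nulls.

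Three stronger readings are tempting and are not supported.

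- A reader might infer that the trial's error rate is 11-14%. That counts primary and secondaries as one family, which the SAP does not expressly promise to hold at 5%. The top of the range also needs uncorrelated endpoints, which is unlikely for cognitive and functional scales measured in the same patients.
- A reader might infer that each low-dose or lower-ranked claim carries twice the stated risk. It does not: each single comparison is still tested at 0.05. What can nearly double is the chance of at least one false claim in the family.
- A reader might infer that the plan allows MMSE to be declared significant after CDR-SB fails. The SAP is silent here and does not say so. The protocol is not at hand and may state the condition. In any case its absence is not the main source of the excess.

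**Conclusion.** The concern holds for the secondary family. The SAP calls the rule closed and says it controls Type I error, but by construction it does not do so strongly. The family-wise rate can reach about 9-10% (9.7% at ρ = 0, 9.2% at ρ = 0.9). This rests on equal allocation with a shared placebo, a common endpoint correlation, and a high-dose MMSE effect large enough to be detected almost surely. Pooling with Study 221AD302 for ADCS-ADL-MCI (section 4.3.3.3) changes the correlations slightly and not the conclusion. Severity is moderate: secondary claims are affected, and the primary analysis and its level are not.

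**What to change.** Leave the primary rule as it is: CDR-SB high dose, then low dose, each at 0.05. Replace the last sentence of the secondary rule with one fixed sequence at 0.05 that stops at the first p > 0.05. Either order controls the secondary family:

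1. MMSE high, MMSE low, ADAS-Cog 13 high, low, ADCS-ADL-MCI high, low; or
2. the three high-dose secondaries in rank order, then the three low-dose ones.

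The second keeps the evident intent that a low-dose failure should not cost the high dose its claims.

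Also state that a secondary is formally tested for a dose only if CDR-SB was significant for that dose. Under the first order, a comparison barred by this condition must end the sequence. If it were skipped, the high dose would again proceed past the low dose at full alpha and the fork would return.

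This restores 5% within the secondary family, not across primary and secondaries together. After a high-dose CDR-SB success, low-dose CDR-SB and high-dose MMSE can still both be open at 0.05, for a maximum of 1 − 0.95² = 9.75%. If joint control is wanted, the SAP should say so and give a graphical procedure with all weights stated. That has a price. If low-dose CDR-SB were tested at 0.025, then on the planning inputs of section 3 (450 × 0.7 = 315 evaluable per group, difference 0.5, SD 1.92) the standard error is 1.92 × √(2/315) = 0.153 and the ratio 0.5/0.153 is about 3.27. Power falls from Φ(3.27 − 1.96) = 90.5% to Φ(3.27 − 2.24) = 84.8%.

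The change is to wording only, and should be made before unblinding. The cost is that secondary results placed after a failed comparison become descriptive. Under the first order this is heavy if the low dose has no effect on MMSE: at most about 5% of trials would get past the second step. Under the second order, low-dose secondary claims require all three high-dose ones to succeed.
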